### **8.3.6 Adverse events of special interest**

An AESI is any AE that a regulatory authority has mandated be reported on an expedited basis, regardless of the seriousness, expectedness, or relatedness of the AE to the administration of a UCB product/compound. For UCB0599, the following events require immediate reporting (within 24 hours regardless of seriousness) to UCB:

- Hy's Law
  - Potential Hy's Law, defined as  $\geq 3$ xULN ALT or AST with coexisting  $\geq 2$ xULN total bilirubin in the absence of  $\geq 2$ xULN ALP, with no alternative explanation for the biochemical abnormality (ie, without waiting for any additional etiologic investigations to have been concluded). Follow-up information should be reported if an alternative etiology is identified during investigation and monitoring of the participant.
- Hypersensitivity reactions (such as rash, angioedema, or anaphylaxis)

### **8.3.6.1 Hypersensitivity reaction monitoring and management**

If a study participant experiences hypersensitivity reaction (such as rash, angioedema, or anaphylaxis), he or she will contact the clinical site immediately (24 hours a day) or seek urgent medical advice in accordance with instructions from the Investigator.

The advice will be based on the clinical presentation and may be to present to the clinical site or seek medical attention in the community.

The study participant should be rapidly and thoroughly assessed in line with actions below.

Hypersensitivity reactions (such as rash, angioedema, or anaphylaxis) will be AESIs and require expedited reporting to UCB, regardless of seriousness, expectedness, or relatedness in line with Section 8.3.6. This will allow for rapid evaluation.

In case of a suspected hypersensitivity reaction (such as rash, angioedema, or anaphylaxis) or any clinical indication of an unexpected immune response, the points described in Sections 8.3.6.1.1 through 8.3.6.1.4 should be observed.

Consideration for restarting study medication is provided in Section 7.1.1.

#### **8.3.6.1.1 Medical history**

Detailed history of the hypersensitivity reaction (such as rash, angioedema, or anaphylaxis) with onset time of symptoms and signs, location of symptoms and signs, first appearance, its evolution (eg, where the rash appeared and to where it spread), any other symptoms (eg, pruritus, swelling, breathlessness, etc) especially if showing a systemic involvement (anaphylaxis), will be recorded. The criteria for anaphylaxis are described in Section 8.3.6.1.1.1.

The clinical progression of the hypersensitivity reactions symptoms should be recorded and any change in symptoms or severity should also be recorded together with the timing.

All AEs reported concurrently should be included within the review.

It will also be important to investigate any recent intake of new medications, herbs, supplements, or the recent use of any topical substances.

#### **8.3.6.1.1.1 Anaphylaxis**

Sampson et al. listed criteria for the diagnosis of anaphylaxis. This was developed at the Second National Institute of Allergy and Infectious Disease/Food Allergy and Anaphylaxis Network symposium (Sampson et al, 2006).

Acute onset=minutes to a few hours.

Criteria for diagnosis-1 or more of the following:

- Acute onset of an illness with symptom complex 1 (see below)
- Acute onset of symptom complex 2 (see below) after exposure to a likely allergen
- Acute onset of a reduced SBP after exposure to a known allergen for the participant.

Symptom complex 1: both of the following:

- At least 1 of the following:
  - Skin involvement (generalized hives, pruritis, flushing)
  - Mucous membrane involvement (swollen lips, swollen tongue, swollen uvula)
- At least 1 of the following:
  - Respiratory compromise (dyspnea, wheezing, bronchospasm, stridor, reduced peak expiratory flow, hypoxemia)
  - Reduced SBP, collapse, syncope, incontinence or other symptom of end-organ dysfunction

Symptom complex 2: 2 or more of the following:

- Skin or mucous membranes (as above)
- Respiratory compromise (as above)
- Reduced BP (as above)
- Persistent gastrointestinal tract symptoms (cramping, abdominal pain, vomiting)

Reduced SBP is indicated by 1 of the following:

- Blood pressure <70% of Baseline SBP
- Age  $\geq$ 11 years AND  $\leq$ 90mmHg

Limitations:

Treudler et al. found that the criteria may not perform as well as others for the recognition of severe, immediate reactions (Treudler et al, 2008).

#### **8.3.6.1.2 Complete physical examination**

Evaluation of a possible hypersensitivity reaction (such as rash, angioedema, or anaphylaxis) includes a complete physical examination of the entire body as soon as feasible after reporting by the study participant. The complete physical examination includes a detailed description of the signs such as rash or angioedema, the location of the signs, and an examination for other possible signs, such as:

- Blanched or flushed skin
- Mucous membrane erosions or ulceration
- Maculae

- Papulae
- Blisters
- Confluent erythema
- Angioedema: face, lips, and/or tongue swelling, also back of hands or feet
- Wheeze, stridor, dyspnea
- Palpable purpura
- Lymphadenopathy

An examination of the entire skin surface, not just local to the site of reaction, is required.

Furthermore, a complete physical examination will also include:

- Vital signs (high fever, dyspnea, or hypotension)

Vital signs (pulse rate, SBP, DBP, respiratory rate, body temperature, and oxygen saturation) will be taken when the AE of hypersensitivity is reported and at regular intervals (approximately 20-30 minutes) for a minimum of 2 hours. The frequency thereafter will be based on clinical judgement. If there is worsening of clinical status, the Investigator will apply the appropriate treatment and safety procedures (eg, call emergency) and contact the UCB Study Physician.

- Photography of rash and other symptoms at the first opportunity and with reasonable time sequence to document resolution. If timely site visit is not possible the participant may be requested to take photos to ensure photos of active symptoms. If participant is requested to provide photos the Investigator should advise the participant in data protection requirements (eg, avoidance of identifying features such as characteristic tattoos, parts of the face). The Investigator will ensure that identifiable characteristics are removed / hidden before sharing the pictures with the Sponsor.
- Re-examination should the symptoms significantly worsen
- Occurrence of other recent or current symptoms, even if they appear not related

### **8.3.6.1.3 Additional investigations**

Investigators should arrange for the following investigations; further investigations may be requested after consultation with the Medical Monitor:

- Additional blood sampling for extended etiological characterization of the hypersensitivity reaction including:
  - Basophil Activation Test
  - Lymphocyte Transformation Test assays
  - Tryptase
  - IgE
- Rapid referral to experts (ie, dermatologist, allergist, or immunologist)

Additionally a skin biopsy should be considered following review by expert.

#### **8.3.6.1.4 Treatment**

Investigators will administer the appropriate treatment as deemed necessary in cases of hypersensitivity. This includes the use of antihistamines for urticaria and the appropriate management in case of potentially life-threatening events such as anaphylaxis, Stevens-Johnson Syndrome, and toxic epidermal necrolysis.

#### **8.3.6.2 Renal function safety monitoring and management**

If a participant develops clinically significant renal dysfunction, repeat laboratory testing should be undertaken as soon as possible and other appropriate investigations may be arranged. An increase in serum creatinine of >25% from the previous value will trigger repeat testing within 48 hours. The Medical Monitor should be notified and consideration should be given to more frequent monitoring.

Clinically significant renal dysfunction will trigger an SMC and DMC review.

Participants must be discontinued from study medication (but not necessarily from the study) if laboratory tests suggest evidence of renal toxicity (see Section 7.2). Any clinically significant findings in laboratory results for renal function will be monitored until resolution or stabilization.

The SMC and DMC charters will include further details regarding the assessment of renal function.

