### **7.2           Participant Discontinuation/Withdrawal from the study**

Participants are free to withdraw from the study at any time, without prejudice to their continued care.

A participant may withdraw from the study at any time at his/her own request, or may be withdrawn at any time at the discretion of the Investigator, SMC, or DMC for safety, behavioral, compliance, or administrative reasons.

If the participant withdraws consent for disclosure of future information, the Sponsor may retain and continue to use any data collected before such a withdrawal of consent.

If a participant withdraws from the study, he/she may request destruction of any samples taken and not tested, and the Investigator must document this in the site study records.

See the Schedule of Activities (Section 1.3) for data to be collected at the time of study discontinuation and follow-up, and for any further evaluations that need to be completed. The DaT-SPECT will occur at EOT (End of Treatment), provided that the previous DaT-SPECT occurred more than 6 months prior to EOT visit.

Participants should be withdrawn from the study if any of the following events occur:

1. Withdrawal of consent by the study participant
2. A regulatory agency requests withdrawal of the participant from the study
3. Loss of ability to freely provide consent through imprisonment or involuntarily incarceration for treatment of either a psychiatric or physical (eg, infectious disease) illness or throughout quarantine conditions.

Participants must be discontinued from study medication (but not necessarily from the study) if any of the following occurs:

1. Study participant develops an illness that would interfere with his/her continued dosing.

2. Study participant takes prohibited concomitant medications as defined in the protocol. Outcome should be decided on a case-by-case basis.
3. There is confirmation of a pregnancy during the study, as evidenced by a positive pregnancy test.
4. Study participant has actual suicidal ideation since last visit as indicated by a positive response (“Yes”) to either Question 4 or Question 5 of the “Since Last Visit” version of C-SSRS. The study participant should be referred immediately to a mental healthcare professional and must be discontinued from study medication.

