5. Study participant is confirmed positive for recreational drug use or for alcohol at a Baseline Visit (Day 0), which is deemed significant enough to impair the study participant’s safety or the quality of the collected data. Outcome should be decided on a case-by-case basis.
6. Renal toxicity considered possibly related to the IMP. Laboratory tests suggestive of renal toxicity which should trigger further assessment may include:
  - Increase in serum creatinine  $\geq 0.3\text{mg/dL}$  OR
  - Increase in serum creatinine to  $\geq 1.5$  times from Baseline OR
  - New persistent albuminuria or clinically significant increase in pre-existing albuminuria, over 6 consecutive weeks

Any clinically significant findings in laboratory results for renal function will be monitored until resolution or stabilization.

7. The Sponsor requests withdrawal of the participant.
8. Study participant takes part in any other interventional study during the duration of this study.

Investigators should contact the Medical Monitor, whenever possible, to discuss the withdrawal of a participant in advance.

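### Protocol 7.2 item 6 sends suggestive renal laboratory results to further assessment, while the matching sentence in 8.3.6.2 makes them a mandatory reason to stop study medication

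*Protocol*

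**What the plan says.** Section 7.2 of the protocol has a list introduced by "Participants must be discontinued from study medication (but not necessarily from the study) if any of the following occurs". Item 6 of that list opens with the event itself: "Renal toxicity considered possibly related to the IMP". The next sentence brings in the laboratory findings with different force: "Laboratory tests suggestive of renal toxicity which should trigger further assessment may include". Three findings follow: a serum creatinine increase of at least 0.3 mg/dL; an increase to at least 1.5 times Baseline; and albuminuria that is new and persistent, or clinically significantly increased, over six consecutive weeks. The first bullet gives no reference value; the second names Baseline.

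Section 8.3.6.2 covers renal monitoring. Its stopping sentence reads "Participants must be discontinued from study medication (but not necessarily from the study) if laboratory tests suggest evidence of renal toxicity", followed by a pointer to Section 7.2. The same section says: "An increase in serum creatinine of >25% from the previous value will trigger repeat testing within 48 hours". It also asks for prompt repeat testing, and allows other investigations, when renal dysfunction is clinically significant. It calls for the Medical Monitor to be notified, sends clinically significant renal dysfunction to the safety monitoring committee (SMC) and data monitoring committee (DMC), and leaves further detail to their charters.

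The Amendment 4 history (Section 10.11.2) explains why item 6 was revised: participants with mild or moderate renal impairment whose fluctuations are clinically insignificant should be able to stay in the study.

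**The concern.** A compulsory stopping rule should give one answer for one result. Here the two sections use nearly the same term, laboratory tests that suggest renal toxicity, and attach different consequences to it. In 7.2 such tests start an assessment, and discontinuation depends on toxicity judged possibly related to study drug. In the 8.3.6.2 sentence the tests alone are enough.

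Two sites with identical results could therefore act differently. Under Section 6.8, a participant whose study medication is stopped early attends the End of Treatment and Safety Follow-up visits and cannot enter PD0055. Exposure to the assigned arm also changes. If renal laboratory changes were more frequent in one arm, the reading a site adopts would influence how much of that arm's assigned treatment is actually taken.

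**Working it through.** **Step 1. The two rules side by side**

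| Element | 7.2 item 6 | 8.3.6.2 stopping sentence |
|---|---|---|
| What requires stopping | Renal toxicity considered possibly related to study drug | Laboratory tests suggesting renal toxicity |
| Relatedness judgement | Yes | Not mentioned |
| Action on a suggestive test | Further assessment | Discontinuation of study medication |
| Pointer | None | To Section 7.2 |

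**Step 2. Does the pointer settle it?** The phrase in 8.3.6.2 matches the words 7.2 uses to introduce the assessment prompts, not the words it uses for the stopping event. A site that follows the pointer arrives at a list in which those same tests call for assessment. Both readings remain available.

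**Step 3. Which way does the stated purpose point?** Amendment 4 gives a reason for the revision of item 6: clinically insignificant fluctuations should not end participation. The literal 8.3.6.2 sentence, which stops study medication on a suggestive test alone, works against that aim.

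**Step 4. The creatinine thresholds (secondary).** The documents give no figure to reproduce. The inputs are the 0.3 mg/dL increase (7.2 item 6) and the trigger of more than 25% from the previous value (8.3.6.2). Assume that the 0.3 mg/dL rise is measured from Baseline, which the bullet does not say, and that the previous value equals Baseline, as at a first post-Baseline test. For a Baseline of b mg/dL, the relative size of the rise is 0.3/b:

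- b = 0.8: 0.3/0.8 = 37.5%, above 25%
- b = 1.2: 0.3/1.2 = 25.0%, not above 25%
- b = 1.5: 0.3/1.5 = 20.0%, not above 25%

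The crossover is 0.3/0.25 = 1.2 mg/dL. On those assumptions, a 0.3 mg/dL rise from 1.2 mg/dL or more does not set off the repeat test. A rise to 1.5 times the same reference is a 50% rise and always does.

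**Step 5. How far the crossover depends on the assumptions.**

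- Baseline 1.5, previous value 1.43: the trigger lies at 1.43 × 1.25 = 1.7875, so it is met at 1.79, before the 0.3 mg/dL criterion at 1.80.
- Baseline 0.80, then 0.95, then 1.10: the steps are 0.15/0.80 = 18.75% and 0.15/0.95 = 15.8%. The total rise is 0.30 with no step above 25%.

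The two criteria are therefore misaligned, but 1.2 mg/dL is not a general boundary between them.

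**The case against.** The best defence is that 8.3.6.2 only summarises 7.2. It cites that section, repeats its formula about stopping study medication but not necessarily the study, and the Amendment 4 rationale supports taking item 6 as the operative rule. That is a plausible account of what was intended. It does not remove the problem, because the summary leaves out the two conditions that decide whether a participant stops.

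A second defence stands in part. A reader might infer that 8.3.6.2 contains no assessment at all, so that a participant loses study drug on one unrepeated value. The documents do not support that for the section as a whole: it provides for repeat testing, Medical Monitor notification and SMC and DMC review. Section 8.2.5 separately requires clinically significant abnormal results to be repeated. These safeguards are tied to clinical significance or to the rise of more than 25%, and the stopping sentence is not made conditional on any of them. The omission is in that sentence, not in the whole section. The charters might add detail, but they are not available here, and investigators work from the protocol.

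A third defence stands. A reader might infer that the thresholds contradict each other, or that from a Baseline of 1.2 mg/dL the 0.3 mg/dL criterion always comes before the repeat test. Nothing makes the repeat test a gate before that criterion. Under 7.2, a participant who meets the 0.3 mg/dL figure is still assessed. The ordering also depends on the assumptions in Step 4 and fails when they change, as Step 5 shows.

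Finally, treatment discontinuation is handled by a treatment-policy strategy (protocol Table 9-2 and Section 9.5.1; SAP Table 1-2), so data collected after stopping stay in the analyses. That limits the effect on the efficacy data set. It does not restore exposure or make conduct uniform.

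**Conclusion.** The inconsistency in action is real as written and rests on no numerical assumption. One renal laboratory result leads to assessment under 7.2 item 6, and to compulsory discontinuation under the literal 8.3.6.2 sentence. The cross-reference does not resolve it, and the literal reading runs against the stated reason for the current item 6.

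The threshold point is secondary: the 0.3 mg/dL bullet lacks a reference value, and the repeat-test trigger uses a different kind of reference. The 1.2 mg/dL figure illustrates this only when the previous value equals Baseline and the rise is measured from Baseline.

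The size cannot be derived. The documents do not give the distribution of creatinine or the expected frequency of renal findings. A reader might try to show from the eGFR limit in exclusion 40b that participants at a particular creatinine level are eligible. The documents name the formula but do not print its coefficients, and 40b and criterion 41 contain other renal exclusions, so no such example is offered. Nor do the documents show that the primary comparison is compromised. The conclusion is limited to a stopping rule that can be applied in two ways.

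**What to change.** The sponsor should reconcile Section 7.2 item 6 with the stopping sentence in Section 8.3.6.2 so that one stated action follows from the listed laboratory findings at every site, and both sections say the same about whether assessment and a relatedness judgement are part of it. In the same edit, the sponsor should check the 0.3 mg/dL wording and the repeat-test wording for consistency. No view is given here on which action, threshold, reference value or order of triggers is right; that is a clinical decision for the sponsor.

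The cost is a change of protocol text and a memo to sites. No additional procedures, visits or participants are needed.

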#### **8.3.7 Anticipated serious adverse events**

The following Anticipated SAEs are anticipated to occur in the population studied in this protocol at some frequency that is independent of drug exposure.

This list does not change the Investigator's obligation to report all SAEs (including Anticipated SAEs) as detailed in Section 8.3.1 and Appendix 3 (Section 10.3).

**Table 8-1: Anticipated serious adverse events for Parkinson's disease population**

MedDRA System Organ Class	MedDRA Preferred Term
Nervous system disorders	Syncope
Psychiatric disorders	Hallucination

MedDRA=Medical Dictionary for Regulatory Activities

#### **8.3.8 Wearable sensor – adverse events (adverse sensor effects, unanticipated adverse sensor effects, SAEs, serious adverse drug events, and unanticipated serious adverse drug events) and sensor deficiencies**

The wearable sensor is being provided as a noninvasive exploratory tool for use in this study for the evaluation of digital measurements for aspects of motor function, sleep, and neurovegetative parameters.

In order to fulfill regulatory reporting obligations worldwide, the Investigator is responsible for the detection and documentation of events meeting the definitions of incident or malfunction that occur during the study with the wearable sensor.

Adverse Events associated with the wearable sensor will be reported to the appropriate regulatory agencies and sensor developer. Adverse event reporting will be conducted as per the specific laws, regulations, directives, standards and/or guidelines as appropriate and as required by the countries in which the clinical investigation is conducted.

The definition of a sensor deficiency can be found in Appendix 7 (Section 10.7).

NOTE: Events fulfilling the definition of an AE/SAE will also follow the processes outlined in Section 8.3.3 and Appendix 3 (Section 10.3).

#### **8.4 Safety signal detection**

Selected data from this study will be reviewed periodically to detect as early as possible any safety concern(s) related to the study medication so that Investigators, clinical study participants, regulatory authorities, and IRBs/IECs will be informed appropriately and as early as possible.

The Study Physician or medically qualified designee/equivalent will conduct an ongoing review of SAEs and perform ongoing SAE reconciliations in collaboration with the Patient Safety representative.

As appropriate for the stage of development and accumulated experience with the study medication, medically qualified personnel at UCB may identify additional safety measures (eg, AEs, vital signs, laboratory or ECG results) for which data will be periodically reviewed during the course of the study.

#### **8.5 Treatment of overdose**

For this study, any administration of UCB0599 totaling greater than 360mg within approximately a 24-hour time period will be considered an overdose.

Overdose events are only considered AEs or SAEs if there are associated clinical signs and symptoms or if the act of taking the excess study medication itself is an AE or SAE (eg, suicide attempt).

UCB does not recommend specific treatment for an overdose.

In the event of an overdose, the Investigator or treating physician should:

- Stop dosing and contact the Medical Monitor immediately.
- Closely monitor the participant for any AE/SAE and laboratory abnormalities until UCB0599 can no longer be detected systemically (approximately 5 days).
- Obtain a plasma sample for PK analysis within 3 days from the date of the last dose of study medication if requested by the Medical Monitor (determined on a case-by-case basis).
- Document the quantity of the excess dose as well as the duration of the overdose in the eCRF.

Decisions regarding dose interruptions or modifications will be made by the Investigator in consultation with the Medical Monitor based on the clinical evaluation of the participant.

